In a two year randomized, pilot study, two exercise training regimens (IMT and Aerobic) will be evaluated as compared to a control group by studying their effect on clinical end points and correlating them with central effects on cardiac remodeling specifically focusing on indices of left ventricular systolic and diastolic function (LVEDV, LVESV, EF, LV mass, LV longitudinal strain e' and E/e). Given that prior studies have predominantly studied aerobic exercise and there is no data available on the effect of IMT on cardiac remodeling or the peripheral effects, this study will provide us the unique opportunity to study IMT to determine its efficacy compared to aerobic training and will also provide mechanistic insight to overall change in symptoms. We anticipate that insights from this work will facilitate clinical implementation of exercise training and potentially provide insight into the use IMT as a therapy in individuals with HF who cannot perform aerobic exercise.

Overall Study Protocol: 75 HF patients will be enrolled. HF diagnosis will depend on physician diagnosis⁶⁵⁻⁶⁸. As part of this protocol 15 control subject will undergo a comprehensive pre- and post- assessments that will include a battery of physical function evaluations (aerobic, strength, and questionnaire indices), quality of life (QoL), and echocardiography. At the conclusion of their initial assessments they will continue with usual clinical care and will be retest on the same battery of assessment 12 weeks later. 60 patients already taking part in the VA MERIT F0834-R will have the option to additionally enroll into this study which would require them after enrollment into the Exercise Therapy protocol to complete an echocardiogram at baseline as well as post-intervention. All other parts of their participation will occur as part of the Exercise Therapy trial.

Table 4: Outline of protocol (by visit) for Controls group

Initial Assessment	Visit 1	Informed consent and physical exam, physical functional assessment battery (aerobic, strength, 6MWT, Hand Grip, and questionnaires), and echocardiographic
Exercise Training	12 weeks	Care as usual
Post assessment	Visit 38	Post-exercise assessment battery will mirror visit 1

Table 5: Outline of protocol (by visit) for Intervention Group

At time of randomization from VA MERIT F0834-R visit 3 of that protocol	Initial Assessment	Visit 1	Informed consent and echocardiographic

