Recruitment for this pilot project will primarily draw from the larger funded Exercise Therapy which is currently enrolling patients.. Once participants have completed the initial baseline visit for the Exercise Therapy study they will be told of this additional study and will be provided the option to participate if they chose to. If they chose to participate they will complete an echocardiogram prior to starting the exercise intervention as part of the Exercise Therapy protocol.

In addition control participants will be recruited through posted flyers (at all VABHS campus), mailings, and in clinic recruitment. In clinic recruitment will occur at the West Roxbury campus at the Heart Failure clinic. [name] is Director of the VA Heart Failure Program, a highly successful clinical program with over 500 HF patients, and a strong track record of recruitment into clinical trials. [name] works with two physician, two nurse practitioners, and two fellows to manage patients in this program, and they have established a track record of working together to identify HF patients who can be invited to participate in trials (consistent with HIPAA guidelines). Moreover, [name] has also organized a comprehensive HF list of patients attached to the HF program over the past 8 years; this has helped grow recruitment efficacy for mailings to potentially eligible patients, and is a recruitment asset that will be used for the proposed trial.

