Echocardiographic Assessment: All echocardiographic assessments will be performed at the West Roxbury VABHS campus where [name] is the Director of the Echo Lab. All subjects will have comprehensive echocardiographic studies in which all traditional echocardiographic parameters will be assessed, including comprehensive assessment of LV/RV structure and both systolic and diastolic function as recommended by the American Society of Echocardiography guidelines^{72,80}. Left ventricular end diastolic and end systolic volumes and ejection fraction (EF) will be measured by 2D (modified Simpson's method)⁷² as well as 3D TTE using an X5 probe and an offline analysis with Q-lab software (Phillips Burlington)⁸⁸ LV mass will be measured by the area length method⁷². For systolic assessments, in addition to traditional indices of LV volumes and EF, novel parameters, including longitudinal strain, strain rate, and LV twist will be measured^{55,87}. Diastolic function assessments will include traditional measures of mitral inflow velocity (E), mitral annular tissue velocity (E'), ratio of E/E', mitral flow propagation velocity as well as isovolumic relaxation time (IVRT) pulmonary venous flow profiles, and LV untwisting rate^{71,87}. Indices will also include measurement of left and right ventricular wall thickness, cavity dimensions, LA volume, right ventricular systolic function, cardiac output as well as pulmonary pressure. Please see appendix 2 for imaging protocol.

Functional Assessments and Exercise Training: Exercise assessments and exercise training for participants taking part in the intervention portion of the proposed study will be based off of and completed as part of the funded VA MERIT F0834-R to which this study is complements. For those that will be controls for the proposed study their assessment will be completed independent of the funded Merit. Functional assessments and training sessions will be completed at the JP VABHS.

The battery of physical function assessments will include aerobic, strength, inspiratory, and questionnaire indices to provide a comprehensive assessment of performance at baseline, after training.

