Those individuals that are in the “intervention group” will also be taking part in the research study “Exercise Therapy”. As part of the “Exercise Therapy” study they will be randomly assigned to one of two exercise interventions (aerobic or Inspiratory muscle training). The differences between outcomes of these two groups will be evaluated in relation to changes within the echocardiogram as part of this study, however the exercise interventions are taking place as part of the Exercise Therapy study for the exercise is detailed below.

Exercise Training: Both aerobic and inspiratory muscle exercise regimens will total 60 minutes in length and will be scheduled 2-3x weekly for 12 weeks. This volume of exercise has consistently been shown to significantly improve functional performance and physiologic measures of interest in HF patients^{3,50,78}. Each exercise regimen will be designed to achieve a similar volume of exercise and to also achieve equivalent social/support dynamics of group training (camaraderie, encouragement). If training sessions are missed, exercise intensity will initially be reduced (using RPE at 13-14 to guide the stimulus) when subjects return, and intensity will then re-advanced over the next 2-3 sessions to make-up for any declines.

Prior to and immediately following all exercise trainings group, a 5-minute warm-up and a 5-minute cool-down period will occur. All participants will under the same the warm-up and cool-down phases during which they will perform slow aerobic (less than 30% of their maximum) and stretching. The warm-ups and cool downs will be matched between groups to ensure that changes seen between groups in outcomes is directly from the exercise type not from any difference format.

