Randomization will be generated using a SAS program based upon permuted random blocks of variable size to assure approximate balance over time and will be stratified by sex and statin use.

Aim 1a: *a) We hypothesize that exercise training will result in a decrease in Left ventricular end diastolic and end systolic volume and increase in ejection fraction (measures of morphology and systolic performance) as compared to the control group. b) We hypothesize that exercise training will increase mitral annular early diastolic velocity (e') as well as decrease the ratio (E/e') of early mitral inflow velocity (E) and e' (measures of diastolic performance). c) We hypothesize that both forms of training will be more beneficial compared to the control group and IMT will be non inferior to aerobic training regimen as related to cardiac remodeling.*

The outcomes for these hypotheses will be the outcome measures at baseline and at the end of follow-up. Parts a & b involve superiority tests using a mixed linear regression model comparing each active treatment group to the control group, specifically the interaction between time and treatment, with the ability to adjust for baseline values of the outcomes. Part c requires a test of non-inferiority between the two active treatments also involving a mixed model with a lower bound of 0.65 standard deviation units for each measure [see Sample Size and Power below].

Aim 2. *To explore the benefits of improved cardiac remodeling and physiology on functional and qualitative exercise training endpoints. a) We hypothesize that exercise training related cardiac improvements will lead to improved aerobic functional parameters (measured as peak VO_2 and VE/VCO_2 slope). b) We hypothesize that exercise training-related cardiac improvements will lead to improved quality of life.*

For hypotheses a & b, baseline and follow-up in peak VO_2 , VE/VCO_2 slope and quality of life will be the outcomes in separate mixed linear regression models using the measures of morphology, systolic and diastolic performance at evaluation times that were used as outcomes in aim 1 as predictors.

Exploratory Aim. Using the outcomes from aim 2 in separate mixed linear regression models using the predictors from aim 1 with the addition of potential confounders of peripheral function as determined by the supporting funded Merit to. We will evaluate the independent effect of central cardiac change on function.

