Patients can also dilute the training effects if they modify their regimen by doing supplemental exercises at home (e.g., adding aerobic exercises by those in the IMT arm of the study). We will emphasize the priority of maintaining precise training regimens, and will offer patients the chance to cross-train as soon as the formal protocol is completed.

Although the current proposal employs well-validated exercise training parameters^{3,40-43, 68}, it is possible that the duration and intensity of the exercise training (either IMT or aerobic) may not be adequate to induce measurable changes in cardiac geometry and or to systolic and diastolic physiological performance.

Human Subjects

A. Risk to Subjects

A. Human Subjects Involvement and Characteristics

The study population will consist of 75 male and female participants age 50 and older who have been diagnosed with systolic heart failure (HF). Recruitment will include only Veterans and will focus on the VA Boston Healthcare System for recruitment. All patients must be cleared by their physician to participate in a supervised exercise environment.

As indicated in the Methods section:

Inclusion Criteria

- NYHA class II or III or AHA stage B or C HF with reduced ejection fraction (≤ 45), or AHA stage C with preserved ejection fraction despite a minimum of 6 weeks of optimal treatment
- Age ≥ 50 years

- Optimal therapy according to AHA/ACC and HFSA HF guidelines, including treatment with ACEI and beta-blocker therapy (for at least 6 weeks), or have documented reason for variation, including medication intolerance, contraindication, patient preference, or personal physician's judgment.
- ✓ Patients using statins will be enrolled; in the pilot study it was evident that most patients eligible for this study were on statins since prevalence of hypercholesterolemia is high and most clinicians are attentive to prescribing statins as part of their standard of care. While this is potentially a confounding issue, we will be certain that statin use is balanced in each arm.

Exclusion Criteria

- Major cardiovascular event or procedure within the prior 6 weeks.
- HF secondary to significant uncorrected primary valvular disease (except mitral regurgitation secondary to left ventricular dysfunction). If valve replacement has been performed, patient may not be enrolled for 12 months after this procedure.
- Dementia
- Severe COPD (FEV1<50%),
- PVD that would limit exercise- End-stage malignancy

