The VA Boston is a large cardiovascular clinical center, encompassing 3 campuses (Jamaica Plain, West Roxbury, and Brockton) and several community based outpatient clinics (CBOC), with a high volume of heart failure seen throughout these campus. The plan will be to recruit 45 patients in year one, and 30 patients during year two, for a total of 75 participants. Primary recruitment for this study will occur as part of the already funded research project VA Merit F0834-R entitled “Exercise Therapy to Reduce Heart Failure Symptoms; Sorting Mechanisms of Benefit” (Site-PI, [name]; PI, [name]). Additionally control subject will be recruited through heart failure clinic, echocardiogram clinic and flyers post.

Only individuals who provide written informed consent may participate. In accordance with informed consent and HIPAA regulations, written informed consent and HIPAA forms will be obtained from each participant after a thorough explanation of procedures by a project staff person and the opportunity for the participant to ask and receive answers to questions. Participants will be informed of the nature of the investigation, the types of assessments and treatment involved, the potential risks involved in participation and will be asked to sign an informed consent statement prior to participating in the proposed study. In addition, participants will receive an explanation of how their information will be handled including all parties involved, data management, and plans to publish data in group format without identifying information. The Institutional Review Board of VA Boston Healthcare System will approve the protocol, consent, and authorization forms. Participants will also be informed that they are free to withdraw from the study at any time without any consequences.

B. Protection Against Risk

We will carefully screen to identify individuals whose risk for potential adverse outcomes is elevated were they to participate in the proposed research. All participants will have a thorough review of their medical records prior to enrolling in the study by study staff and study physicians. To determine stability prior to beginning exercise all participants will have a physical exam performed by a study cardiologist, physician or nurse, complete an exercise stress test that will be administered by trained personnel and supervised by a cardiologist, physician, or nurse practitioner.

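### The controls are recruited separately and not randomised, so the exercise-versus-control tests in Aim 1 are non-randomised concurrent comparisons and should be labelled, adjusted and interpreted as such

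*Combined protocol and SAP*

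**What the plan says.** The opening of Materials and Method labels the design: "In a two year randomized, pilot study, two exercise training regimens (IMT and Aerobic) will be evaluated as compared to a control group". The sections that follow describe two separate routes into the study.

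- **Exercise groups.** Under Overall Study Protocol, "60 patients already taking part in the VA MERIT F0834-R will have the option to additionally enroll into this study". Under Functional Assessments and Exercise Training, the text says that within the parent trial "they will be randomly assigned to one of two exercise interventions (aerobic or Inspiratory muscle training". Table 5, the intervention schedule, mentions randomisation.
- **Controls.** Under Recruitment, "In addition control participants will be recruited through posted flyers (at all VABHS campus), mailings, and in clinic recruitment". Recruitment and Consent Procedures repeats this: "Additionally control subject will be recruited through heart failure clinic, echocardiogram clinic and flyers post". They continue usual care and are retested at 12 weeks. Table 4, their schedule, has no randomisation step. On testing, "For those that will be controls for the proposed study their assessment will be completed independent of the funded Merit".

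Statistical Analysis specifies permuted blocks of variable size, stratified by sex and statin use, without naming the arms covered. For Aim 1a/b it plans superiority tests in a mixed model "comparing each active treatment group to the control group", through the time-by-treatment interaction, with adjustment for the outcome's baseline value available as an option. Sample Size and Power treats each comparison as a t-test of 30 against 15. The Human Subjects inclusion criteria say of statins that "we will be certain that statin use is balanced in each arm". Limitations covers recruitment, attrition, extra exercise at home and training dose, but not how the control group is formed.

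**The concern.** Exercise versus control is the superiority question of Aim 1, and it is planned with a stated alpha, power and detectable difference. A reader of the design sentence would take it for a randomised contrast. Yet the exercisers had already joined a trial requiring 12 weeks of sessions two to three times a week, while the controls answered a flyer or mailing or were approached in clinic, and agreed only to be tested twice. The two groups could differ in willingness to train, referral source, disease stage or changes in medication. Any of these could affect how cardiac measures move over 12 weeks.

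The stratified blocks cannot balance a group that does not pass through them, and an intention-to-treat analysis preserves only the balance that randomisation created. What is at stake is whether a difference from control may be reported as an effect of training. Both regimens are compared with the same 15 controls, so a selection effect in that group would enter both comparisons. Agreement between them would not be independent confirmation.

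**Working it through.** **1. Is there any route by which a patient could be randomised to control?** Set side by side, the sections give:

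| Feature | Exercise groups | Controls |
|---|---|---|
| Source | Merit participants who opt in | Flyers, mailings, clinics |
| Assignment | Random, aerobic or IMT | None described |
| Functional testing | Within Merit | Outside Merit |
| Schedule | Table 5, mentions randomisation | Table 4, no randomisation step |

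No section allows assignment to control. That the controls are not randomised is an inference from these statements, but it is the only reading they support.

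**2. What does the planned model remove?** With two time points and complete data, the time-by-treatment interaction is the difference in mean change, (post − pre) in exercisers minus (post − pre) in controls. A baseline difference that stays constant cancels. A difference in expected 12-week change that would exist without training does not; it is added to the estimate. Aim 1 names no other covariate and no matching. The confounders mentioned in Statistical Analysis are peripheral-function measures and belong to the Exploratory Aim.

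**3. The plan's own figure.** Inputs from Sample Size and Power: 30 and 15 patients, alpha 5%, 80% power, 0.91 SD. Sidedness is not stated; two-sided is used here. Noncentrality = d / √(1/30 + 1/15) = d / √0.1; df = 30 + 15 − 2 = 43; critical t = 2.017. At d = 0.91 the noncentrality is 0.91 / 0.3162 = 2.88 and power is 80.3%. The exact detectable difference is 0.906 SD, so 0.91 reproduces. It would be the same if the same 30:30:15 split were randomised: sample size is not the issue.

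**4. Illustration of bias.** Let selection alone shift the change by b SD. The documents give no value for b, so the sizes below are assumptions. If training does nothing and the bias favours exercise, the test behaves as if the true difference were b. If training truly has a 0.91 SD effect and the bias runs against it, the test sees 0.91 − b.

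| Assumed b (SD) | Noncentrality, b / 0.3162 | Rejection, inert programme | Power at true 0.91 SD, bias against exercise |
|---|---|---|---|
| 0 | 0 | 5.0% | 80.3% |
| 0.2 | 0.63 | 9.5% | 59.3% |
| 0.3 | 0.95 | 15.3% | 47.1% |
| 0.5 | 1.58 | 34.0% | 24.5% |

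In the third column nearly all rejections at b > 0 favour exercise: 9.0, 15.1 and 33.9 percentage points respectively, against 2.5 points with no bias.

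**The case against.** The strongest reply is that this is a pilot meant to inform later research, and that adding a concurrent control group to a separately funded trial is a legitimate pilot design. Both groups share eligibility criteria, a requirement for at least 6 weeks of optimal therapy or a documented reason for variation, an examination for stability, one health system and one echocardiography laboratory. The interaction term removes stable baseline differences. The bias sizes above come from no document and could run either way. All of this stands. It limits how much confounding to expect and rules out saying that selection would drive the result; the supportable word is could. It does not make the comparison randomised, and a pilot that sets powered superiority tests should say what those tests can show.

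Some stronger readings are tempting but not supported:

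- *The study is not randomised at all.* A reader might infer this from the design sentence. But aerobic versus IMT is randomly assigned, so the label is right for that contrast and for the non-inferiority part of Aim 1c. Table 5 places consent to this study at the time of randomisation, and the documents do not settle which comes first; that does not show the randomised contrast to be compromised.
- *The statin-balance promise is false for controls.* It is unsupported rather than shown false. The statement may refer to the randomised arms only, and the same paragraph says most eligible patients take statins, so any imbalance may be small.
- *Matching and a long covariate list are required.* With 15 controls, matching on several factors and adjusting for many covariates is more than the data can carry. Baseline EF would also duplicate the baseline outcome when EF is the outcome.

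**Conclusion.** The point holds in a limited form. Aim 1a/b and the better-than-control part of Aim 1c rest on a non-randomised concurrent comparison that the plan neither labels as such nor lists as a limitation, and for which it offers only optional adjustment for the baseline outcome. The size of any bias is unknown. Under assumed shifts of 0.2 to 0.5 SD, the nominal 5% error rate becomes 9.5% to 34.0%; shifts of the same size against exercise reduce 80% power to between 59% and 25%. These figures assume a two-sided t-test of 30 against 15 with complete data. They illustrate sensitivity and do not estimate what will happen. The conclusion itself rests on the separate recruitment and the two-way randomisation as written.

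**What to change.** 1. **Label and limit.** In Materials and Method and in Statistical Analysis (Aim 1), call exercise versus control a non-randomised concurrent comparison, and keep the word randomised for aerobic versus IMT. Add this to Limitations. Word conclusions from Aim 1a/b, and from the control part of Aim 1c, as associations. This step matters most, because willingness to train cannot be adjusted away with the measures collected.
2. **Pre-specify adjustment.** In the Aim 1a/b model make adjustment for the baseline outcome mandatory, and name a short covariate list from data already collected: for example age, statin use, and either baseline EF or peak VO2, chosen so that it does not repeat the outcome's own baseline. Report the unadjusted estimate as a sensitivity analysis, together with a baseline table of controls against exercisers. When groups differ at baseline, the adjusted and unadjusted estimates can disagree, so the primary one should be fixed before analysis.
3. **Statins.** Restrict the balance statement in the Human Subjects inclusion criteria to the randomised arms.

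Matching controls as they are recruited is optional. The cost is protocol and SAP wording, weaker causal language and a few degrees of freedom: with the baseline outcome and three covariates in an equivalent regression for one comparison, residual df falls from 43 to 45 − 2 − 4 = 39.

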Project Time Line

Year I →→→→→	Year II →→→→→
Start Recruiting	Continue Recruiting
Start Assessments	Assessments
Start EX sessions	Exercise Sessions
	Manuscript Preparation

Year	Year 1		Year 2	
Time frame	0-6M	6-12M	12-18M	18-24M
Staffing	ES, RA, EX	ES, RA, EX	ES, RA, EX	ES, RA, EX
Enrollment	15	20	20	10
What will be happening	Setup/purchase supplies/recruitment/initial assessment /	Recruitment/assessments/interventions	Recruitment/Assessments/interventions	Recruitment/Assessments/interventions / manuscripts preparation

Study Team: Throughout the trial, [name] will meet regularly with co-investigators (4 times a year initially, and increasing to monthly when data analysis begins). Drs. [name], [name], [name], [name], [name], [name] all work in the VA or within close proximity and can presumably come to the VA campus for these meetings. However, phone teleconferencing will also be available for those who cannot participate in person. The skillsets and backgrounds of the investigators (as detailed in their biosketchs and the budget section) are extremely complementary and have contributed to a collegial and productive dynamic.

All study staff that will be working on this project are currently on staff at the VABHS. The echo sonographer, research assistant, and exercise physiologist will be an integral part of the team, they will coordinate recruitment, participant screening, enrollment, perform assessment visits, and follow ups. The current VABHS infrastructure through the Clinical Studies Unit (CSU) provide the ability for one exercise physiologist to perform the functional assessment while another performed the exercise trainings. This will allow this physiologist to remain blinded to the subject's intervention group thus eliminating tester bias.

Statistical Analysis: General considerations: This is a pilot study, described below are continuous outcome measures, primarily changes in function outcomes and gene expression and either continuous or categorical predictors. In all instances, outcome variables will be evaluated for violation of model assumptions and transformation of these variables will be considered as a remedy if needed. Analyses will generally be performed with an intent-to-treat approach, with sensitivity analyses performed to assess the role of drop-outs on the results.

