All echocardiographic examinations will be performed at the West Roxbury VA campus by well trained sonographers. West Roxbury VA echo lab is a fully accredited lab by ICEAL. All echocardiographers performing the examination are board certified and credentialed by ICEAL. Standard echocardiographic equipment will be used and image acquisition will be performed in accordance with the standards proposed by the American Society of echocardiography. Patient privacy and confidentiality will be maintained during the entire procedure. Efforts will be made to keep the environment and support by staff to be reassuring and pleasant.

Standard echocardiographic examination is non invasive and therefore there are no inherent risks associated with this procedure. However about 10% of the patients may not have adequate acoustic window for image acquisition. In this group of patients intra-cavitary echo contrast will be used for better endocardial border delineation. Contrast will be administered through a peripheral IV.

- Risks associated with this will include the inherent risks of a peripheral IV and risks associated with contrast administration which are as follows. Rare allergic reactions at an approximate rate of 1/10,000,
- Other adverse effects include headache, weakness, fatigue, palpitations, nausea, pruritus and back pain. Potentially life threatening reactions could occur although very rare. (In our laboratory we perform >4000 echo per year and use contrast in at least 10% of our pts. In the last 8 years we have never had a single serious reaction).

Contraindications for administration of contrast include

- a) right-to-left, bidirectional, or transient right-to-left cardiac shunts
- b) hypersensitivity to perflutren
- c) hypersensitivity to blood, blood products, or albumin (applies to Optison only).

2. Adequacy of Protection from Risk

A. Recruitment and Consent Procedures

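### No blinding to group or visit is stated for acquiring or reading the echocardiograms, although every Aim 1 outcome is an echo measurement

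*Combined protocol and SAP*

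**What the plan says.** The Study Team section (under Project Time Line) contains the only blinding provision. It relies on having "one exercise physiologist to perform the functional assessment while another performed the exercise trainings", and concludes: "This will allow this physiologist to remain blinded to the subject's intervention group thus eliminating tester bias". This concerns functional testing.

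The same section describes the staff: "The echo sonographer, research assistant, and exercise physiologist will be an integral part of the team, they will coordinate recruitment, participant screening, enrollment", and the list goes on to assessment visits and follow-up. The duties are given to the three roles jointly.

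On the echocardiograms:

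- Human Subjects, Therapeutic Risk, covers acquisition: "All echocardiographic examinations will be performed at the West Roxbury VA campus by well trained sonographers". It mentions accreditation and credentials but no masking.
- Echocardiographic Assessment covers measurement. Volumes and ejection fraction come from 2D and 3D imaging with "an offline analysis with Q-lab software". It does not say who reads the studies, how many readers there are, or whether they know group or visit. It refers to Appendix 2 for the imaging protocol.

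Statistical Analysis, Aim 1a, tests left ventricular volumes, ejection fraction, e' and E/e' at baseline and end of follow-up through the time-by-treatment interaction. Aim 2 uses the same echo measures as predictors.

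**The concern.** The plan recognises tester bias as a threat and addresses it for the functional tests, which supply the Aim 2 outcomes. It makes no matching provision for the echo measurements, which carry Aim 1.

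Volumes, ejection fraction and strain depend partly on which frame is chosen and where borders are traced. The hypotheses are directional: smaller volumes, higher ejection fraction, higher e' and lower E/e' after training. A reader who knows that a study is a 12-week scan of a trained patient could, without intending to, read it in the expected direction. Because Aim 1 compares changes between groups, such a shift enters the estimated effect directly. Participants cannot be blinded to exercise, and enrolling more patients would not remove a measurement bias.

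**Working it through.** **Who could know what, from the documents**

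| Comparison | Points towards knowledge of group | Points against |
|---|---|---|
| Exercise vs control | Controls come through flyers, mailings and clinics (Recruitment) and follow their own visit schedule (Tables 4 and 5). The sonographer is among the staff coordinating recruitment and follow-up. | Duties are listed jointly, not person by person. |
| IMT vs aerobic | Nothing in the plan prevents it. | Allocation is made within the Merit study, training is at the JP campus and echo is at West Roxbury. |
| Baseline vs 12 weeks | No removal of dates or visit labels is described. | Data are coded, but the stated purpose is confidentiality. |

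**Reproducing the plan's power figure**

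Inputs from Sample Size and Power: 30 per active group, 15 controls, 0.91 SD, 80% power, alpha 5%. Sidedness is not stated; two-sided reproduces the figure.

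- Standard error in SD units: √(1/30 + 1/15) = 0.3162
- Degrees of freedom: 30 + 15 − 2 = 43, critical t = 2.017
- Noncentrality: 0.91 / 0.3162 = 2.878
- Power from the noncentral t: 80.3%, in agreement with the plan

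**Effect of an assumed reading bias**

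The documents give no size for reader bias, so a range is used. Let b be the bias in the difference in mean change, in SD of the change score, favouring training, with no true effect. The false-positive rate is P(|T| > 2.017), where T is noncentral t on 43 degrees of freedom with noncentrality b / 0.3162.

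| b (SD of change) | Noncentrality | Two-sided false-positive rate |
|---|---|---|
| 0 | 0 | 5.0% |
| 0.1 | 0.316 | 6.1% |
| 0.2 | 0.632 | 9.5% |
| 0.3 | 0.949 | 15.3% |

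**The unit matters**

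If the shift is expressed in SD of a single reading, it must be divided by √(2(1 − ρ)), where ρ is the baseline-to-12-week correlation. The plan does not give ρ. For shifts of 0.2 and 0.3 reading SD:

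- ρ = 0.2: divisor 1.265, rates of about 8% and 11%
- ρ = 0.5: divisor 1, rates of 9.5% and 15.3%
- ρ = 0.8: divisor 0.632, rates of about 16% and 31%

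**IMT versus aerobic**

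With 30 versus 30 and one-sided 5%, the standard error is √(2/30) = 0.2582. The 0.65 SD margin gives noncentrality 2.517 and 80.0% power, again the plan's figure. If IMT were truly worse by exactly the margin, a bias of 0.1, 0.2 or 0.3 SD towards IMT would raise false non-inferiority from 5% to about 10%, 19% or 31%. This rests on a further assumption, that the reader knows the arm, for which the documents give less support.

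**The case against.** The strongest reply is that the documents are silent, and silence is not evidence of unblinded reading. That stands. A reader might infer that the sonographer and readers are unblinded, but no section says so. Appendix 2 is a natural place for reading rules and is not in the supplied text. The staff list says nothing about who reads the images, and the sonographer's share of the joint duties could be limited to assessment visits.

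A reader might also infer that all Aim 1 comparisons are equally exposed. The documents do not support that: the separation of training site and echo laboratory gives IMT versus aerobic some protection, although it does not guarantee masking.

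A third tempting inference is that the functional tester must know who is a control. Functional Assessments and Exercise Training says: "For those that will be controls for the proposed study their assessment will be completed independent of the funded Merit". It does not say who tests controls or what that person is told. This strand would in any case bear on Aim 2 outcomes, for which no exercise-versus-control contrast is specified.

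Two further replies carry less weight. Coded data protect confidentiality, but coding does not hide group or visit from someone measuring images. The study is called a pilot, but it specifies powered superiority and non-inferiority tests.

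Finally, masked reading addresses measurement bias only. It would not make controls recruited by a separate route comparable with the trained patients.

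**Conclusion.** The point holds as a gap in the plan. Followed as written in the supplied text, the plan leaves the Aim 1 contrasts open to reader bias, most plausibly for exercise versus control and less certainly for IMT versus aerobic. The conclusion is subject to whatever Appendix 2 contains.

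The rise to about 6%, 9.5% or 15% is illustrative. It assumes a bias of 0.1, 0.2 or 0.3 SD of the change score, no true effect, and a t-test standing in for the mixed model, as in the plan's own power calculation. It is neither an estimate nor a bound, and it should not be cited as a property of this trial. The remedy is simple enough that the sponsor should adopt it without waiting for a better estimate of the bias.

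**What to change.** 1. If Appendix 2 already masks echo reading, say so in Echocardiographic Assessment. Otherwise add a rule there.
2. Store every echo study under the coded ID, with name, date and visit removed. Have the existing echo laboratory reader or readers measure baseline and 12-week studies of all three groups offline, in random order, blind to group and visit.
3. State in Statistical Analysis that these readings are the Aim 1 data. The same values would then serve as the Aim 2 predictors.
4. In Study Team, limit the phrase "thus eliminating tester bias" to the functional tests, where the tester is kept separate from training.

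The cost is relabelling work and later availability of echo results. Masked reading does not blind acquisition. Keeping the acquiring sonographer away from contact that reveals group would help where feasible, but it is not clearly free: the time line lists only three staffing codes (ES, RA, EX), so those coordination duties would have to be reassigned.
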